Sexual Health Empowerment for Jail-Involved Women's Health Literacy and Prevention

NCT # 03984695

June 28, 2023

SHE-WOMEN PROTOCOL

SIGNIFICANCE OF PROJECT

Public health problem and opportunity. On any given day, one million women are under criminal justice supervision in the U.S.¹³ Criminal justice policies in the U.S., linked to the ‘War on Drugs’ initiated nearly 50 years ago, have had a disproportionate impact on poor women, Black and Brown women, and women with complex trauma, mental health, and drug problems.¹⁴ The criminal justice policies themselves result in stark class, race, and gender disparities when it comes to who gets incarcerated.¹⁵ Indeed, the incarceration of women has increased at a rate double that of men for the decades since the War on Drugs was initiated.¹⁶

Because the U.S. incarcerates the most disenfranchised women in the country, mass incarceration has become a *de facto* driver of women’s health disparities.¹⁷ Women face health disparities related especially to their long trauma histories, ongoing drug use, and participation in the sex trade economy.¹⁸ The U.S. also incarcerates women who, because of their poverty, lack of participation in the formal employment sector, and ongoing stints of incarceration, are least likely to have health insurance, primary care doctors, or usual places for medical care, all predictors of engagement in preventive health services that mitigate women’s health problems.¹⁹ Women who become incarcerated also have low levels of educational attainment to begin with, and we have found that their low levels of health literacy, in particular, may explain their health disparities.³ They simply do not have high levels of women’s health knowledge; they have varying beliefs about women’s health practices and screening; and they have multiple barriers to self-efficacy for negotiating prevention and getting the health care they need.³

Our prior work has focused on addressing these women’s health disparities. For example, we work to narrow *cervical cancer disparities*, since women with criminal justice involvement have 4-5 times the rates of cervical cancer compared to the general population.⁴⁻⁶ Jailed women may also face *breast cancer disparities*, as only 40% of age-eligible jailed women are up to date on breast cancer screening, compared to 79% in the general population.^{7-8,20} There are *disparities in unintended pregnancy* as well, with up to 84% of jailed women reporting unintended pregnancy, while only about 49% of women in the general population do so.^{21,22} Finally, women with criminal justice histories bear the burden of *sexually transmitted infection (STI) disparities*, with higher rates of HIV, syphilis, Chlamydia, and gonorrhea, compared to the general population.^{23,24,25} Our goal is to address these disparities through a comprehensive women’s health literacy intervention.

Progress report for this study. To address just one of these women’s health disparities, in 2014 we received funding to evaluate the effectiveness of a jail-based cervical health literacy intervention, Sexual Health Empowerment (SHE) for Cervical Health Literacy and Cancer Prevention, on changing the women’s cervical health knowledge, beliefs, and self-efficacy, and confidence for screening and prevention (R01 CA181047, [name] (PI), 04/01/2014 – 03/31/2019). The first aim of the study was to assess the impact of a sexual health empowerment intervention (SHE Project) on cervical health knowledge, barriers to screening that are related to beliefs about cervical cancer, and self-efficacy for screening and follow-up among women leaving jail. Using a three-year observational design employing both survey and ethnographic methods for follow-up, the second aim of the study was to understand how knowledge, beliefs, self-efficacy, and other factors change post-release cervical health prevention behaviors over time. We published a paper in 2014 that described the need for the intervention and laid out intervention components.²⁶ We published a paper in 2015 operationalizing a definition for cervical health literacy – that is, women’s knowledge, beliefs, and self-efficacy for cervical cancer screening.³ From September 2014 to March 2016, we consented 261 women to participate in the jail and group-based 10-hour intervention, running 29 separate intervention groups. We followed up with a paper in 2017 showing that among the 182 women who completed the intervention in jail (we lost about one-third of consented women primarily due to jail turnover), cervical health literacy increased in 7/8 domains for participants in the experimental group, compared to the waitlist control group.⁴ Our follow-up rates annually over the last three years have averaged an exceptional 85% with this incredibly hard-to-reach group of women. We currently have a paper in press describing our team’s outreach and follow-up strategy.¹² Another paper published in 2018 described the rich theoretical framing of our intervention, using both social theory and feminist scholarship to undergird the content.²⁷ We have also completed our one-year post-intervention outcomes paper that showed that more women were up to date on cervical cancer screenings compared to baseline and that the best predictors for up to date Pap screenings were age, public benefits, medical insurance, along with cervical cancer knowledge, benefits, barriers, seriousness, and susceptibility (i.e., cervical health literacy).²⁸ Interestingly, we found that women who also went for STI screening after jail had greater increases in cervical health literacy in 5/8 domains, suggesting that components of the original SHE intervention extended to other women’s health outcomes.

Women who consented to participate in SHE had several women's health risk factors, as shown in Table 1. During execution of SHE, we observed: 1) the cross-cutting nature of women's health risk factors, i.e. the risks that jailed women faced for cervical cancer also could lead to other women's health problems; and 2) an opportunity for taking a now evidence-based intervention, with a rich theoretical framing, to expand to other women's health issues faced by this group of women, around, not only cervical cancer prevention, but also breast cancer, unintended pregnancy, and STI prevention. *It is this opportunity that is the focus of this study.*

We took advantage of a study team that included public health graduate students, medical students, and NIH diversity supplement trainees on SHE to start building out the other intervention components. We also leveraged relationships with local organizations to start piloting intervention content. In SHE, we had already built out the cervical health literacy content. Using the same health literacy framework and theoretical underpinning, we built and integrated components for age and risk appropriate breast cancer, birth control, and STI literacy. With departmental funds, a university fellowship supporting a medical student and funding from NCI through a diversity supplement to the parent SHE grant (R01CA181047-S2, [name], Trainee), we have begun piloting the new intervention components. We have run three cycles of the birth control literacy curriculum with women in a local domestic violence shelter. Though the sample size is small (N=25), we showed gains in birth control literacy, and have made necessary changes to the content based on the piloting.²⁹ We have conducted focus groups with 32 women to help build content for STI literacy. We also developed breast cancer literacy content and have manuscripts under review in each of these three areas.^{7,10,28} Most papers describe health risks, while some, like the birth control literacy paper, describes the piloting of our intervention. During summer 2018, while this proposal is under review, one of the diversity supplement trainees ([name], an MD who specializes in sexual health) will work with the SHE Project Director (who was the primary SHE health educator) to integrate content for all four areas of our new intervention, SHE-Women (Table 2). SHE-Women will specifically target cervical, breast cancer, birth control, and STI literacy, screening, and risk reduction.

Table 1. Justice-involved women's health risk, N=261	N (% or SD)
Cervical cancer risk	
No Pap test in past 3 years	59 (22.6)
Lifetime abnormal Pap test	126 (48.2)
Cervical cancer diagnosis	30 (11.4)
Breast cancer risk	
No mammogram for 50 or older (N=23) in past 2 years	11 (47.8)
Unintended pregnancy risk	
Lifetime unintended pregnancy	207 (79.3)
No past month birth control use (excluding hysterectomy)	76 (29.1)
Sexually transmitted infection risk	
Lifetime STI history	163 (62.4)
No condom use at last sex	196 (75.1)
Ever sold sex	91 (34.8)
Cross-cutting risk factors	
Past month tobacco use	205 (78.5)
Alcohol use problem	132 (50.5)
Past year drug dependence	163 (62.4)
Lifetime mental health diagnosis	191 (73.1)
Past year intimate partner violence	133 (50.9)
Uninsured	160 (61.3)
No primary care doctor	150 (57.4)
No medical home	70 (26.8)
Lifetime months incarcerated, Mean	24.2 (45.3)
Race/ethnic group with higher cancer mortality	
e.g. Black	83 (31.8)
e.g. Hispanic	21 (8.0)
Age, Mean	33.7 (±9.9)

Table 2. SHE-Women - A women's health literacy curriculum

Knowledge of cervical, breast cancer, birth control, and STIs	Beliefs about cervical, breast cancer, birth control, and STIs	Self-Efficacy for cervical, breast cancer, birth control, and STI screening	Confidence navigating health systems for screening and risk reduction
Female body anatomy Medical terminology How stuff works in the body, prevention, and cures Procedures Costs	Beliefs about disease Beliefs about screening Where you learned about sex/health/prevention? What do you share with kids, partners? Romantic/sexual relationship dynamics Experiences with providers Motivations for screening and prevention	What is self-efficacy? Do you know where to go for services/experiences at these places/barriers? Do romantic/sexual partners get in the way/help? How to get results? What makes it easy to get services? Drug use/ homelessness/ transportation/ financial/ other barriers – how to overcome?	Confidence navigating providers given long-term criminal justice involvement? Jail health care and services, trust, cost Outside of jail services, trust, cost, fears Insurance/no insurance Social support for health care seeking Coercion

We hypothesize that SHE-Women, like the original SHE intervention, will be effective at increasing women's health literacy, screening, and risk reduction practices among the vulnerable group of women leaving jail. To test this hypothesis, the first goal of this study is to assess the effectiveness of the broadened SHE-Women intervention. Our study addresses the health disparities faced by women leaving jail, and the relative lack of evidence-based programming for this group of vulnerable women.

A second goal of this study is to test intervention modality. SHE-Women will rely on an integrated, mediated electronic platform to deliver content and engage participants.³⁰ Delivery of the original SHE intervention required daily entry into the jail for 5 days per intervention cohort. Two health educators needed to be present. While there were advantages to this approach (group context, building rapport, conversation), there were challenges associated with access to the jails, costs for staffing, and replicability across criminal justice facilities. Thus, in this study we will test the effectiveness of an integrated, multimedia electronic women's health literacy intervention delivery program through a text and Web platform.³¹ To support a trial of this new modality, our diversity supplement trainee collected data on the feasibility of offering the intervention in a text-Web platform to 32 jailed women. The trainee found that women access the internet daily when in the community and have interest in an electronic women's health platform with access to health professionals via the platform. In another study, we found that 88% of our participants had a mobile phone; 76% sent and received text messages, and 50% accessed the Web on their phones. About 79% of the women said they used internet regularly – with most citing internet use at the public library, home, or from their mobile phones. Seventy percent had Facebook accounts. Many of the participants stayed in touch with our outreach team through text messaging. They texted the PD/former health educator a day or two after their release, suggesting that they knew us, trusted us, and looked to keep in touch after jail.¹² For example, 40% of participants regularly engaged with us through a closed Facebook group, post-intervention. This rapport is reflected in an 85% follow-up rate even three years post-intervention. In this study, our data supported the movement of SHE-Women to an integrated, multimedia electronic women's health literacy intervention delivery program through a text and Web platform. If such an electronic sexual health educational program is effective, for future projects, we can create an intervention model that is replicable across other groups of high-risk women in the community.

It is worth noting that 80% of women with criminal justice involvement are *in the community*, rather than confined. Thus, for the purposes of reducing this population's health disparities, an intervention modality that works for vulnerable women *in the community* has the greatest potential utility. Because of our history of working with women leaving jails, we are also uniquely positioned to conduct a trial that tests the effectiveness of an integrated, multimedia electronic women's health literacy intervention delivery program in this context.

Our third goal is focused on investigating the role and impact of trust and rapport that health educators build with participants during behavioral interventions. Although we did not measure trust and rapport in the original SHE study, we always commented about the "[name] effect" on participants – [name] being the name of our lead health educator, and the ways in which the women responded positively to her. We also realize that although fitness apps and electronic interventions are extremely popular, many miss the potential benefit of integrated human interaction with a health "expert."³¹ Thus, our study formalizes the measurement of perception and impact of human interaction in behavioral and electronic interventions. [name] has been awarded a diversity supplement (NIH R01CA181047-S1 [name]). The overall goal will be to develop an electronic literacy intervention focused on the prevention of cervical cancer through implementation of HPV catch-up vaccination among criminal legal system (CLS)-involved women aged 27-45. The aims of this supplement are as follows:

- 1) Assess the interest and needs for adapting and implementing an HPV catch-up vaccine module for the SHE-WOMEN.
- 2) Create and pilot an electronic HPV vaccination catch-up module for women with criminal legal system involvement.
- 3) Evaluate the impact of the electronic HPV vaccination catch-up module in a sample of 25 women.

For this supplement, [name] will work with [name] and the SHE-WOMEN study team to conduct formative interviews (N~40) with women in the target population. Women will be recruited from within the ongoing SHE-WOMEN RCT. Eligibility will be based on age – targeting the 27-45 age group – with a focus on recruiting women who have NOT received HPV vaccine. A

A verbal consent will be read, and an informed consent will be provided if the participant requests. Participants will participate in a 20–30-minute semi-structured interview. Interviews will be recorded with the participant's consent. They will be paid \$10 for their participation in interviews. Participants may stop at any time, if they do not want to complete the interview.

To evaluate the impact of the electronic HPV vaccination catch-up module, [name] will have 25 women look at content for a new HPV vaccine module, then ask questions about their demographics, HPV knowledge, beliefs and vaccination receipt. Participants will be paid \$25 for completion of the survey.

[name] has been awarded the Clendening Fellowship funded by the KU School of Medicine. The aim of her project is to assess the experiences and perspectives of women who utilized health services in jails and prisons. For the project, [name], will work with [name] and the SHE-Women study team to contact 20 current SHE-Women participants by phone or Zoom using a random list. She will ask a set of questions to do more in depth inquiry into jail health care experiences. Each participant will be paid \$25 for their interview, which we estimate will last 20-30 minutes each. A verbal consent asking, "Would you be interested in answering a few questions about any health care you received while you were in jail or prison?", will be read before the interview.

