Aim 1 pilot and Aim 2 RCT effectiveness outcomes data will be collected in surveys at baseline and post-intervention for Aim 1, and then also at 1, 2, and 3 years for Aim 2. For Aim 1, depending on the method of re-consenting original SHE participants (over the phone or in person), study staff will conduct the baseline assessment either over the phone or in person using a Web link on the SHE-Women study Website. The Web link to the survey will utilize audio computer-assisted self-interview (ACASI) technology, where the computer device will read the questions and answer options aloud as participants move through the assessment. Study staff will make themselves available in person or by phone to guide participants through the Web survey, if they desire this service. Participants will have the option to turn off audio if they cannot gain access to headphones or are in a public place. To facilitate use of ACASI, participants will be offered free headphones at study start, and then at quarterly check-ins, or follow-up surveys. We have used ACASI with other hard to reach low literacy populations with success (active drug users and with women leaving corrections in other cities). For the Aim 2 RCT, study staff will conduct the baseline assessment using the same Web link to the SHE-Women study Website so that participants become accustomed to survey administration using a secure Web link. Participants randomized to the control arm will not have access to any intervention content on the Website. All other surveys – post-intervention, and 1-, 2-, and 3-year follow-up surveys, will be administered using the same Web link to an ACASI-administered survey. Participants will always be given the option of completing the survey over the phone or in person with a member of the study staff, if that is their preference. If participants become re-incarcerated during the longitudinal follow-up, we can conduct surveys in person or through the mail with paper and pencil copies of the survey – we have previously employed these techniques.

Aim 3 perceptions and uptake data will be collected using the same methods described above for Aim 1.

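### The HPV catch-up module's impact is to be judged from a survey taken only after viewing, so no change in knowledge or beliefs can be estimated

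*Combined protocol and SAP*

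**What the plan says.** The HPV supplement is described near the end of Significance of Project. Its third aim reads: "Evaluate the impact of the electronic HPV vaccination catch-up module in a sample of 25 women". The procedure for that aim takes one sentence: the trainee "will have 25 women look at content for a new HPV vaccine module, then ask questions about their demographics, HPV knowledge, beliefs and vaccination receipt". Payment is "for completion of the survey", in the singular. No effect size, precision target or analysis is given for the 25.

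The supplement's other activity is to "conduct formative interviews (N~40) with women in the target population". The recruitment text follows directly: "Women will be recruited from within the ongoing SHE-WOMEN RCT". "Eligibility will be based on age" (27 to 45 years), "with a focus on recruiting women who have NOT received HPV vaccine". None of this is repeated where the 25 module viewers are introduced, and no restriction by randomized arm or RCT visit is stated.

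For the RCT itself, Data collection says: "Participants randomized to the control arm will not have access to any intervention content on the Website".

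**The concern.** Impact means a difference: between before and after, or between women who saw the module and women who did not. The procedure supplies neither. A score taken once, after viewing, mixes what the women already knew with whatever the module added, and nothing in the design separates the two.

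Vaccination receipt has a further problem. Being vaccinated takes time after seeing the module, and no interval is stated. Asked straight after viewing, the item records vaccination that happened earlier. If the preference for unvaccinated women also applies to the 25, the item would mostly return no, whatever the module does.

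At stake is the supplement's third aim. A high post-viewing score could be reported as evidence that the module works when the data cannot show it.

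**Working it through.** **1. The plan's own figure.** The only figure is n = 25. No inputs are given for it, so there is nothing to reproduce.

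**2. What post-only data identify.** The target is change = (level after) − (level before). The plan collects the first term only. Suppose 15 of 25 (60%) answer an item correctly after viewing. The prior levels below are assumptions, because the document gives none:

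| Assumed level before | Level after | Implied change |
|---|---|---|
| 20% | 60% | +40 points |
| 40% | 60% | +20 points |
| 60% | 60% | 0 |
| 80% | 60% | −20 points |

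The same observed result fits a large gain, no effect or a loss.

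**3. What the survey can deliver.** It can describe the level after viewing. For example, 13/25 = 52% has an exact (Clopper-Pearson) 95% interval of 31% to 72%. A mean score has a 95% half-width of t(0.975; 24)/√25 = 2.064/5 = 0.41 SD.

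**4. Whether RCT data could stand in as the baseline.** Table 5 lists a Pap knowledge scale, a health-belief scale on cervical cancer and Pap testing, screening self-efficacy, and questions on Pap, HPV co-testing and abnormal-Pap follow-up. It lists no item on HPV-vaccine knowledge or receipt. As documented, the RCT surveys cannot supply the missing measurement, even for women who are in the RCT.

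**5. The team's practice elsewhere.** For the small Aim 1 pilot, Table 3 and Data collection specify surveys at baseline and after the intervention. The HPV module evaluation omits the first of these without explanation.

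**6. What a pre-viewing survey would add.** With 25 complete pairs, a paired t-test at two-sided 0.05 has 80% power for a standardized mean change (mean change divided by the SD of the changes) of dz = 0.584. If the repeated-measures correlation r = 0.46 from the Power section is assumed to apply, this equals 0.584 × √(2 × (1 − 0.46)) = 0.584 × 1.039 = 0.61 SD of the score. There would still be no comparator.

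**7. Control-arm exposure, only if the 25 come from the RCT regardless of arm.** With about 100 women per arm, the expected number of controls is 25 × 100/200 = 12.5 (95% range 8 to 17 for a random draw). That is 12.5/100 = 12.5% of controls. This is a share of women possibly exposed, not an estimate of dilution. Dilution also depends on how far an HPV-vaccine module moves the Pap-based cervix outcomes, and on whether viewing precedes the RCT assessments. The document gives neither.

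**The case against.** The best defence is one of scale. This is a 25-woman add-on within a supplement that also sets out to create and pilot the module. No hypothesis test is attached, and no RCT outcome depends on it. If the work were labelled acceptability or descriptive, most of the defect would go. That is fair, and it is one of the two remedies below. It does not rescue the current text, which claims an evaluation of impact.

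The wording also leaves the interval between viewing and questions open, so it is too strong to say that receipt can only reflect earlier behaviour. But no later contact is described either. A same-sitting before-after comparison lacks a control and invites a testing effect; this stands, and it limits what the remedy can claim.

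A reader might go further and infer that the 25 are RCT participants, that controls will see content they are meant not to have, and that the RCT's cervix comparison is materially diluted. The document does not support this:

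- The sentence on recruiting from the RCT follows the interviews and is not repeated for the 25. The fellowship project described next does name current participants explicitly, so RCT membership of the 25 is a plausible reading, not a stated fact.
- Where the module is hosted and when it is viewed relative to RCT visits are not stated, so a breach of the rule on Website access is not shown.
- HPV vaccination is not among the RCT outcomes in Table 5.
- Controls already receive a print booklet with the intervention content, and both arms may text the health educator and attend community sessions.

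Nor does dividing 12.5 exposed controls by the roughly 75 per arm left at year 3 give a worse exposed share. That would assume no exposed control is lost. At Table 4's retention of 150/200 = 75%, 12.5 × 0.75 = 9.4 of 75 remain, which is again 12.5%.

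**Conclusion.** The concern holds for the module evaluation. Followed as written, the plan yields no estimate of change in HPV knowledge or beliefs, because there are no pre-viewing measurements and no comparison group. Receipt asked at that point mostly records past vaccination. This conclusion needs no numerical assumption. It rests on the described procedure being complete; a stretch of the document after the fellowship paragraph was not available to read and cannot be judged.

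The link to the RCT is secondary and conditional. The source of the 25 should be stated. If they are RCT women, some controls may be exposed, but any dilution is probably small and confined mainly to the cervix domain. The document supports no percentage for it. A reader should not conclude that the RCT is compromised.

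**What to change.** Choose one of two routes for the supplement's third aim.

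- **Keep the impact aim.** Ask the HPV knowledge and belief items immediately before and immediately after viewing. Report the mean within-woman change with its confidence interval, labelled as an uncontrolled before-after result. Record vaccination receipt as baseline status. For the outcome, use intention to be vaccinated, or receipt asked again at a later contact that is already scheduled. If the women are in the RCT, that contact could be an annual follow-up survey; the quarterly check-ins are limited to verifying contact details.
- **Drop the impact aim.** Describe the sub-study as acceptability work and report the post-viewing answers descriptively.

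In either case, state where the 25 come from. If they are RCT participants, either use women who have finished their RCT assessments, or record each woman's arm and viewing date and repeat the cervix analyses without post-viewing visits as a sensitivity analysis.

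The cost is a few repeated items, a slightly longer survey, a possible testing effect, and a sentence or two on sampling. Waiting for women to finish their RCT assessments could delay recruitment to the supplement.
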